1.2.7.3.1 KCP-330-004 Study Design

This is a multicenter, Phase 2, open-label study to evaluate the safety and efficacy of Selinexor in approximately 57 patients with recurrent WHO Grade 4 glioma (glioblastoma, glioblastoma multiforme [GBM], and subvariants) (NCT01986348). Patients in Arms A and B receive Selinexor 50 mg/m² (80-90mg/dose) for 4 weeks per 4-week cycle. Patients in Surgical Arm A receive an additional 3 doses of Selinexor prior to surgery and resume Selinexor after recovery. Patients in Arm C receive Selinexor 60 mg bi-weekly (BIW) and patients in Arm D receive 80 mg weekly for 4 weeks per 4-week cycle. Primary end point was 6-months PFS rate.

This study has been re-activated to add 12 patients. Study enrollment will close when 75 patients are enrolled.

1.2.7.3.2 KCP-330-004 Efficacy Results

Selinexor had reasonable brain penetration as shown by significant intra-tumoral selinexor concentrations in surgical specimens (Arm A) [23]. The average tumor concentration was 136nM compared to a plasma concentration of 836nM for a tumor/plasma ratio of 0.14 (N=6).

In the most recent efficacy analysis, the overall response rate (ORR) was 13% in Arm B, 0% in Arm C, and 8 % in Arm D [24]. The 6 months PFS rate was 17% in Arm B, 8% in Arm C, and ~20% in Arm D [24]. The toxicity profile for Arm B 50mg/m² (80-90mg/dose) twice a week was high and thus two additional arms C and D were added with bi-weekly dosing of 60mg for Arm C, and once weekly dosing of 80mg for Arm D. Arm C (60mg BIW) had one grade 3 DLT of fatigue and Arm D (80mg QW) had one grade 3 DLT of lymphopenia. No grade 4 or 5 DLT were seen with the once weekly dosing schedule.

1.2.8 Studies with Selinexor and Radiation

There are no clinical studies with Selinexor and radiation.

1.2.9 Updated Clinical and Efficacy Results (IB version 10, dated 9/21/2020)

Results from ongoing and completed clinical studies have shown that selinexor induces durable antitumor responses across a broad range of relapsed or refractory (RR) hematologic and solid tumor cancers, which is consistent with its proposed mechanism of action. In general, these effects appear to be independent of tumor type or prior treatment(s).

As of 31 March 2020, 3419 patients with hematologic or solid-tumor malignancies had received at least 1 dose of selinexor; in addition, 301 patients received at least 1 dose of selinexor or blinded study treatment (i.e., selinexor or placebo) for a total of 3720 patients. These 3720 patients include 2310 patients from Company-sponsored trials (CSTs; 2009 who received selinexor and 301 who received blinded study treatment), 1201 active patients from Investigator-Sponsored Trials (ISTs) who received selinexor, and 161 patients from the selinexor Expanded Access Program (EAP) who received selinexor; and 9 and 39 patients who received selinexor through clinical trials sponsored by Ono Pharmaceutical Co., Ltd and Antengene, respectively.

The most commonly reported treatment-emergent adverse events (TEAEs) for selinexor in CSTs were nausea (66.1%), fatigue (56.7%), anorexia (includes MedDRA “decreased appetite”; 51.1%), thrombocytopenia (51.0%), anemia (43.5%), vomiting (38.7%), and diarrhea (36.6%), that were generally low-grade and reversible. The TEAEs of thrombocytopenia and anemia, which can be higher grade, were reported primarily in patients with hematologic malignancies.

1.2.9.1 KCP330012/STORM

Based on activity observed for selinexor in combination with dexamethasone in RRMM in Part 2 of the Study KCP330012/STORM (hereafter referred to as STORM), selinexor received accelerated US Food and Drug Administration (FDA) approval in July 2019 for the treatment of adult patients with relapsed or refractory multiple myeloma who have received at least 4 prior therapies and whose disease is refractory to at least 2 PIs, at least 2 immunomodulatory agents, and an anti-CD38 monoclonal antibody. The objective response rate (ORR) was 26.2%, with a quick median time to first response of 4.1 weeks (range: 1 to 14 weeks). The median progression-free survival (PFS) was 3.7 months and median overall survival (OS) was 8.4 months.

1.2.9.2 KCP330-023/ BOSTON

Study KCP330-023/ BOSTON (hereafter referred to as BOSTON) evaluating selinexor plus bortezomib plus lowdose dexamethasone (SVd) vs bortezomib and dexamethasone alone (Vd) in RRMM in which the SVd arm showed a clinically and statistically significant improvement for PFS compared to the Vd arm (median PFS 13.93 months vs 9.46 months) serves as a confirmatory study of the accelerated approval asserting that the responses observed in the STORM study are highly likely to confer clinical benefit. A supplemental new drug application (sNDA) was submitted to the FDA in May 2020 seeking full approval for selinexor as a treatment for patients with MM after at least 1 prior line of therapy.

1.2.9.3 KCP-330-009/SADAL

Selinexor has shown activity in diffuse large B-cell lymphoma (DLBCL) in Study KCP-330-009/SADAL (hereafter referred to as SADAL), a multi-center, single-arm Phase 2b study. Based on the results of this study, selinexor received approval from FDA in June 2020 for the treatment of adult patients with RR DLBCL, not otherwise specified, including DLBCL arising from

follicular lymphoma, after at least 2 lines of systemic therapy. In this study, the ORR was 28.3%, median duration of response (DOR) was 9.3 months and median OS was 9.1 months.

Study XPORT-DLBCL-030 was agreed as the confirmatory trial for evaluating selinexor in DLBCL. This trial will assess the effect of selinexor or placebo added to a standard backbone immunochemotherapy of rituximab-gemcitabine-dexamethasone-platinum (R-GDP) in patients with 1 to 3 prior treatments for DLBCL.

1.2.10 Rationale for Dose Level 2 and 3 Modification (amendment version date: 03/26/2021)

We are using Selinexor as a radiation sensitizer. In theory, it would be more effective if we gave it more frequently as radiation is given 5-days per week. However, we did not have sufficient clinical data to support multi-dosing per week when the trial was originally written. We now have that data and are thus requesting the change. The once-a-week dosing was supported by the FDA approval of Selinexor in the treatment of multiple myeloma (80mg weekly). The new data supporting the twice a week dosing (BIW) is from ARM C of the recently reported KING trial [23]. The KING trial is a Phase 2 study of Selinexor monotherapy in recurrent glioblastoma multiforme. In that trial 14 patients were treated with 60mg BIW with a similar side effect profile to the 80mg once per week given in ARM D. Additionally, in the pre-surgical ARM A of the KING study 6 patients were dosed with 50mg/m², 2-3 hours prior to surgical resection. 136nM of Selinexor was measured within the tumor and is consistent with the desired CNS dose in animal models. Thus, 60mg BIW should give adequate penetration of the CNS, allowing additional fractions of radiation to be sensitized with an equivalent side effect profile. The company has additional unpublished data from a trial in patients with lymphoma with twice weekly dosing (60mg BIW) which has recently received FDA approval.

Thus, we have changed dose levels 2 and 3 in our trial from once-a-week dosing to twice a week dosing.

2 ELIGIBILITY ASSESSMENT AND ENROLLMENT

2.1 ELIGIBILITY CRITERIA

2.1.1 Inclusion Criteria

2.1.1.1 Histological diagnosis

- Pathologically confirmed glioblastoma or gliosarcoma (including astrocytoma, grade IV)

2.1.1.2 Patients must be eligible for definitive external beam radiotherapy and temozolomide.

2.1.1.3 Age \geq 18 years. Because no dosing or adverse event data are currently available on the use of Selinexor in combination with temozolomide in patients <18 years of age, children are excluded from this study.

2.1.1.4 Patients should have a KPS greater than or equal to 70 (see [Appendix A](#)).

2.1.1.5 Absolute neutrophil count (ANC) $>1.5 \times 10^9/L$; platelet count $>100 \times 10^9/L$; and hemoglobin (Hb) >9.0 g/dL. Note: the use of transfusion or other intervention prior to cycle 1 day 1 to achieve Hb >9.0 g/dL is acceptable.

2.1.1.6 Ability of subject or Legally Authorized Representative (LAR) to understand and the willingness to sign a written informed consent document.

2.1.1.7 The effects of Selinexor on the developing human fetus are unknown. For this reason and because Selinexor agents as well as other therapeutic agents used in this trial are known to be teratogenic, women of child-bearing potential and men must agree to use adequate contraception (hormonal or barrier method of birth control; abstinence) prior to study entry, for the duration of study treatment and for one month after treatment. Should a woman become pregnant or suspect she is pregnant while she or her partner is participating in this study, she should inform her treating physician immediately.

2.1.1.8 Patients must have had surgery and/or biopsy not greater than 8 weeks prior to initial evaluation to be eligible for this study.

2.1.2 Exclusion Criteria

2.1.2.1 Patients who are receiving any other investigational agents and have had prior therapy including:

- Patients who have previously received radiation therapy (RT) to the brain.
- Patients who received chemotherapy for the treatment of their glioma
- Patients who are being treated with implanted gliadel wafers
- Patients who are being treated with tumor treating fields

2.1.2.2 History of allergic reactions attributed to compounds of similar chemical or biologic composition to selinexor or temozolomide used in study.

2.1.2.3 Patients with coagulation problems and medically significant bleeding in the month prior to start of treatment (peptic ulcers, epistaxis, spontaneous bleeding). Prior history of DVT or PE is not exclusionary

2.1.2.4 Patients with active uncontrolled or suspected infections

2.1.2.5 Patients with severe liver dysfunction defined as:

- Total bilirubin $> 1.5 \times$ upper limit of normal (ULN) Note: Subjects with Gilberts syndrome should not be excluded as long as total bilirubin is $< 3.0 \times$ ULN and documentation to support diagnosis is available.
- Serum glutamate pyruvate transaminase (SGPT) or called as Alanine aminotransferase (ALT) $\geq 3 \times$ ULN = 135 U/L; for the purpose of this study, the ULN for SGPT is 45 U/L
- Serum glutamic oxaloacetic transaminase (SGOT) or called as Aspartate aminotransferase (AST) $\geq 3 \times$ ULN = 150 U/L; for the purpose of this study, the ULN for SGOT is 50 U/L
- Serum albumin $\geq 2 \times$ ULN

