Abbreviated Title: Selinexor and Radiotherapy

Version Date: 06/30/2025

Abbreviated Title: Selinexor and Radiotherapy

NIH Protocol #: 20-C-0027

Version Date: 06/30/2025

NCT Number: NCT04216329

Title: A Phase I Clinical Trial of Selinexor (KPT-330) in Combination with Temozolomide and Radiation Therapy in Patients with Newly Diagnosed Glioblastoma

NCI Principal Investigator: [name]
Radiation Oncology Branch (ROB)
Center for Cancer Research (CCR)
National Cancer Institute (NCI)
[name]
[name]
[name]
[contact]
Email: [contact]

| | | |
|---------------|------------------------------|-----------------|
| Drug Name: | Selinexor (KPT-330) | Temozolomide |
| IND Number: | 144383 | 144383 |
| Sponsor: | CCR, NCI | CCR, NCI |
| Manufacturer: | KaryoPharm Therapeutics Inc. | Generic |
| Supplier: | KaryoPharm Therapeutics Inc. | NIH CC Pharmacy |

Commercial Device: Radiation

PRÉCIS

Background:

- Although radiation has been shown to improve outcomes in patients with glioblastoma (GBM), median survival remains poor. Even with the addition of temozolomide (TMZ) to surgical resection and radiotherapy, most GBMs will recur in field or adjacent to the high dose radiation volume.
- High rates of local failure indicate that GBM cells *in situ* are relatively radioresistant and that the effectiveness of GBM radiotherapy would benefit from additional radiosensitization.
- Selinexor has recently been shown to enhance the radiosensitivity of glioma cells both *in vitro* and *in vivo*.

Objectives:

- Assess the safety, tolerability, and maximum tolerated dose of selinexor when combined with temozolomide and radiotherapy in patients with newly diagnosed glioblastoma and gliosarcoma.

Eligibility:

- Men and women greater than 18 years old
- Histologically confirmed newly diagnosed glioblastoma or gliosarcoma
- Karnofsky Performance Scale (KPS) ≥ 70
- Patients who have not previously been treated with chemotherapy or radiation therapy

Design:

- This is a Phase I trial to determine the safety and tolerability of selinexor in combination with external beam radiation therapy (RT) and temozolomide in patients with newly diagnosed glioblastoma or gliosarcoma using a “3 plus 3 design,” and three dose escalation levels, with 3 patients per dose level (provided no DLT), a maximum of 21 patients will be enrolled.

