14.1.2.2 Common side effects ($\geq 1\text{-}10\%$)

In 100 people receiving selinexor about 1 to 10 people may have:

- Rash
- Eye disorders including cataract (new or worsened), dry eye, visual impairment, seeing flashes of light.
- Night sweats
- Dry mouth
- Stomatitis – a condition that causes painful swelling and sores inside the mouth
- Dyspepsia – indigestion
- Chills
- Hypotension – low blood pressure
- Hypertension
- Tachycardia – fast heart rate
- Nosebleed
- Contusion (bruise due to body injuries such as fall)
- Electrolyte disturbances including:
 - Low phosphate which may cause muscle weakness and fatigue
 - Low magnesium which may cause muscle twitches and cramps
 - Low calcium which may cause numbness and tingling in the hands/feet/face, muscle stiffness and cramps

- High potassium which may cause muscle weakness, palpitations, or irregular heartbeats and chest pain.
- Low albumin-a specific type of protein in blood (which may cause swelling especially of the hands/feet, weakness, or exhaustion)
- Peripheral neuropathy - weakness, numbness and pain from nerve damage, usually in the hands and feet
- Decrease in lymphocytes – a specific type of white blood cell that are part of your immune system
- Increase of creatinine in the blood due to a reduction in kidney function, often related to dehydration
- Elevated liver enzymes, which indicates destruction of the liver cells, including alanine aminotransferase increased, aspartate aminotransferase increased, blood alkaline phosphatase increased.
- Elevated pancreatic enzymes including high amylase and high lipase
- Muscle weakness
- Febrile neutropenia – fever in the absence of a normal white blood cell response that may mean you have an infection
- Urinary tract infection
- Pain in the joints and muscles
- Malaise (a general feeling of being ill or bodily weakness)
- Muscle spasms
- Gait disturbance
- Hair loss
- Itching
- Depression
- Syncope – fainting
- Sepsis (including septic shock) – potentially life-threatening complication of an infection
- Cognitive disorder- brain disorder in which thinking abilities are impaired.
- Mental status changes including confusion

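### Two exclusion criteria need rewording: the albumin limit in 2.1.2.5 points the wrong way, and the stem of 2.1.2.1 is ambiguous and conflicts with the précis on prior therapy

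*Combined protocol and SAP*

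**What the plan says.** **Liver function.** Section 2.1.2.5 opens with "Patients with severe liver dysfunction defined as" and gives four limits:

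- total bilirubin above 1.5 × ULN, with an allowance for Gilbert's syndrome;
- ALT at or above 3 × ULN, where "for the purpose of this study, the ULN for SGPT is 45 U/L";
- AST at or above 3 × ULN, where "for the purpose of this study, the ULN for SGOT is 50 U/L";
- "Serum albumin" at or above 2 × ULN, in full "Serum albumin $\geq 2 \times$ ULN".

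Albumin is in the screening chemistry panel (2.2.2). The only albumin abnormality named elsewhere is a low value: the selinexor side-effect list in 14.1.2.2 has "Low albumin-a specific type of protein in blood". No lower albumin limit for entry appears anywhere.

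**Prior therapy.** The stem of 2.1.2.1 reads "Patients who are receiving any other investigational agents and have had prior therapy including". Four bullets follow: radiation to the brain, chemotherapy for the glioma, implanted wafers, and tumor treating fields. The précis lists as eligible "Patients who have not previously been treated with chemotherapy or radiation therapy", with no link to investigational agents. The inclusion criteria in 2.1.1 do not themselves require newly diagnosed or untreated disease. The title, the primary objective (1.1.1) and the cohort table (2.3.1) do restrict the trial to newly diagnosed disease.

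**The concern.** Both items are entry criteria with a safety purpose, and neither says what its context shows was meant.

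The albumin limb has the multiple-of-ULN form that suits bilirubin and the transaminases. For albumin the protocol's own concern is a low value, so a limit above normal is inert for the purpose stated in the criterion's heading.

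In 2.1.2.1 the joint stem makes exclusion depend, on a literal reading, on two things being true together. Someone applying the numbered criterion would reach a different answer from someone applying the précis.

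At stake is who enters cohorts of 3 to 6 patients, all treated to 60 Gy, where two DLTs stop escalation (3.1.5). In groups that small, one patient outside the intended population can affect the dose decision. The documents give no basis for saying how often that would happen.

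**Working it through.** **Step 1. The sound limbs of 2.1.2.5.** The stated cut-offs reproduce from the stated ULNs: ALT 3 × 45 = 135 U/L; AST 3 × 50 = 150 U/L. Both match the text, so the fault is confined to albumin.

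**Step 2. The albumin limb.** The criterion fires only if albumin ≥ 2 × ULN. A low or normal value is by definition no higher than the ULN, so it cannot satisfy this whatever the laboratory's ULN. For scale, the documents give no albumin ULN; assuming 4.5 to 5.5 g/dL, the threshold is 2 × 4.5 = 9.0 to 2 × 5.5 = 11.0 g/dL. Example values of 2.0 and 4.0 g/dL both pass. Reversing the inequality sign alone would not repair the line, because the reference would still be twice the upper limit.

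**Step 3. The stem of 2.1.2.1.** There are four combinations of the two conditions:

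| Other investigational agent | Prior therapy | Joined by *and* (as written) | Each sufficient alone |
|---|---|---|---|
| no | no | not excluded | not excluded |
| no | yes | not excluded | excluded |
| yes | no | not excluded | excluded |
| yes | yes | excluded | excluded |

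The literal text excludes one combination of four; separate conditions exclude three. The second row is where the literal text departs from the précis. The third row leaves a patient already on another investigational agent unexcluded at entry, although section 4 bars such agents during active treatment.

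**Step 4. Scope.** Even with each bullet read on its own, 2.1.2.1 and the précis differ. The précis bars previous chemotherapy or radiation therapy without limit of site or disease; the bullets cover radiation to the brain and chemotherapy for the glioma. A patient given chemotherapy for another disease fails the précis and passes 2.1.2.1.

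**Step 5. Effect on the dose-finding figures.** Section 10.2 gives escalation probabilities by true DLT rate p. Under the 3.1.5 rule the formula is (1−p)³ + 3p(1−p)² × (1−p)³. At p = 10% to 60% this gives 0.906, 0.709, 0.494, 0.309, 0.172 and 0.082, matching the stated .91, .71, .49, .31, .17 and .08. The eligibility wording changes none of them.

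**Step 6. Illustration on assumed rates.** Suppose one of the first three patients has DLT risk r and every other patient, including any second group of three, has 20%. Then:

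- P(0 of 3) = 0.8² × (1−r)
- P(1 of 3) = r × 0.8² + (1−r) × 2 × 0.2 × 0.8
- P(escalate) = P(0 of 3) + P(1 of 3) × 0.8³

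| r | P(0 of 3) | P(1 of 3) | P(escalate) |
|---|---|---|---|
| 20% (all alike) | 0.512 | 0.384 | 0.71 |
| 40% | 0.384 | 0.448 | 0.61 |
| 60% | 0.256 | 0.512 | 0.52 |
| 80% | 0.128 | 0.576 | 0.42 |

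The relevant quantity is P(escalate), not P(0 of 3), because one DLT in three leads to three more patients rather than to stopping.

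**The case against.** The strongest reply is that neither fault lets in the patients a reader might fear.

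- **Liver.** A reader might infer that patients with severe liver dysfunction are not excluded. That does not follow: three of the four limbs work. The side-effect entry in 14.1.2.2 also describes a drug effect, not an entry threshold, so it supports the intended direction only indirectly.
- **Prior therapy.** A reader might infer that prior brain radiation excludes only in combination with an investigational agent, and so that previously irradiated patients will enter a 60 Gy cohort. The documents do not support this. Each bullet under 2.1.2.1 is phrased as a complete description of a patient, and two are in the present tense, which does not fit a stem about past therapy; staff may well treat them as separate exclusions. Patients must also be eligible for definitive radiotherapy and temozolomide (2.1.1.2) and have had surgery or biopsy within 8 weeks of initial evaluation (2.1.1.8). An investigator takes the history, and pathology is reviewed centrally (2.2.2).
- **Dose finding.** No passage links low albumin or prior radiation to DLT risk, and a DLT must be at least possibly related to selinexor (3.1.4).

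All of this stands as a limit on the consequence. It does not make the albumin line meaningful, nor does it remove the disagreement between 2.1.2.1 and the précis. Clear intent elsewhere is a reason to make the criterion say it.

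**Conclusion.** The point holds in two parts of unequal strength. The albumin limb is wrong as written: it can never flag low albumin, whatever the ULN, and no other criterion sets a lower limit. The stem of 2.1.2.1 is ambiguous; its literal reading conflicts with the précis, and the scope of its bullets differs from the précis even on the charitable reading. Entry of a previously irradiated patient is possible under the literal text but unlikely given the rest of the protocol.

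The stronger inference, that such patients would enter and determine the maximum tolerated dose, is not supported. The fall from 0.71 to 0.52 (0.61 to 0.42 for an assumed risk of 40% to 80%) rests wholly on assumed DLT rates and shows only how sensitive a small cohort is to one atypical patient. The planned sample size and the published 3+3 probabilities are unaffected.

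**What to change.** - In 2.1.2.5, correct the albumin limb so that its direction matches the criterion's heading, or delete it. Any cut-off is for the clinical team; the documents give none.
- In 2.1.2.1, list concurrent investigational agents and each prior therapy as separate exclusions, each sufficient alone.
- Reconcile the scope of those exclusions with the précis (any previous chemotherapy or radiation, or only glioma chemotherapy and brain radiation) and use the same scope in both places.
- At the same time, check 2.1.2.3, which joins coagulation problems and recent significant bleeding with the same kind of *and*.

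The cost is a short wording amendment and an update of any eligibility checklist. No analysis, sample size or escalation rule needs to change.

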2.1.2.6 Known active hepatitis A, B, or C infection

2.1.2.7 HIV patients are not eligible because of their immunocompromised status and overlap of side effects between HAART therapy and radiation therapy.

2.1.2.8 Patients must not have significantly diseased or obstructed gastrointestinal tract malabsorption, uncontrolled vomiting or diarrhea, or inability to swallow oral medication

2.1.2.9 Pregnant women are excluded from this study because Selinexor could have the potential for teratogenic or abortifacient effects. Because there is an unknown but potential risk for adverse events in nursing infants secondary to treatment of the mother

with Selinexor, breastfeeding should be discontinued if the mother is treated with Selinexor. These potential risks may also apply to temozolomide used in this study.

2.1.2.10 Patients with pre-existing known or suspected radiation sensitivity syndromes will be excluded due to potential confounding effect on outcome.

